10.4 Analysis of Vital Signs

Vital sign measurements of systolic and diastolic blood pressures (sitting and standing), pulse rate (sitting and standing), respiratory rate, body weight, orthostatic systolic blood pressure, orthostatic diastolic blood pressure, and orthostatic pulse rate will be summarized.

Each vital sign variable will be summarized by treatment group for all time points (starting with Baseline) with the number of non-missing observations, mean and standard deviation, median, Q1, Q3, minimum and maximum. Mean change from baseline to each applicable post-baseline visit will be summarized for each vital sign variable by treatment group, with the number of observations, baseline mean, and visit mean. The change from baseline mean, and standard error will be presented for the mean change from baseline within each treatment group.

Vital sign variables will be evaluated based on potentially clinically significant (PCS) criteria ([Appendix C](#)). For each vital sign PCS criterion, the number and percentage of subjects who have a vital sign value meeting the criteria will be summarized. Listings will be provided to summarize subject-level vital sign data for subjects meeting PCS criteria.

10.5 Other Safety Analyses

10.5.1 Electrocardiograms

Descriptive statistics for ECG parameters (i.e., heart rate, PR interval, QRS interval, RR interval, QT interval, and QTc interval) at baseline, postbaseline, and changes from baseline values at each postbaseline timepoint will be presented by treatment group.

ECG parameter values are considered PCS if ECG values meet either the actual value or change from baseline PCS high criteria listed in [Appendix C](#), Table C-4. The number and

percentage of subjects with PCS postbaseline values will be tabulated by study treatment. The percentages will be calculated relative to the number of subjects with at least 1 postbaseline assessment. The numerator will be the total number of subjects with an more extreme (worse) postbaseline value than the baseline value. If a subject did not have a baseline value but met the criterion post-baseline, then the subject is counted in the numerator. Subject is counted once if the criterion is met more than once. A supportive listing of subjects with PCS postbaseline values will be provided. A listing of all AEs for subjects with PCS ECG values will also be provided.

The number and percentage of subjects meeting each of the criteria for postbaseline ECG values of clinical interest listed in [Appendix C](#), Table C-5 will be summarized. Subjects will be counted only once for the most severe category. A supportive listing of subjects with postbaseline QTcF increases > 30 msec will be provided, including the PID number, study center, and all QTc values (including changes from baseline). A listing of all AEs for subjects with postbaseline QTcF increases > 30 msec will also be provided.

A shift table from baseline to the end of double-blind treatment period and active treatment extension period in the investigator's overall interpretation of the ECG will be presented by treatment group for the following categories: normal; abnormal, not clinically significant; abnormal, clinically significant for Safety Population 1 and Safety Population 2, respectively. A tabular display of subjects with postbaseline clinically significant ECG abnormalities according to the investigator's overall interpretation will be provided.

10.5.2 Columbia-Suicide Severity Rating Scale

For C-SSRS, the number and percentage of subjects with suicidal ideation or suicidal behavior as recorded on the C-SSRS will be summarized by treatment group for the Safety Populations 1 and 2. The distribution of responses for most severe suicidal ideation and most severe suicidal behavior in the subject's lifetime history, in the past 6 months, in the double-blind treatment period, active treatment extension period, and in the follow up period will also be presented by treatment group. Supportive listings will be provided and

will include the PID number, study center number, treatment group, lifetime history, and postbaseline values. Intensity of suicidal ideation and suicidal behavior type will also be included in these listings.

11.0 Interim Analyses

No interim analysis of efficacy data is planned for this study.

An external DMC composed of persons independent of AbbVie and with relevant expertise in their field will review unblinded safety data from the ongoing study. A separate DMC charter will be prepared and will describe the roles and responsibilities of the DMC, frequency of data reviews, planned interim analyses and relevant data to be assessed, and expectations for blinded communications.

12.0 Overall Type-I Error Control

The Hochberg procedure¹⁰ will be used to control the overall Type I error rate at a 0.05 level (2-sided) for multiple comparisons of each atogepant dose with placebo for the primary endpoint. Detailed procedure is provided below.

Let $p_{(1)}$, $p_{(2)}$, and $p_{(3)}$ denote the nominal p-values in increasing order from the 3 comparisons of atogepant doses versus placebo.

- Step 1: If $p_{(3)}$ is ≤ 0.05 , then all the 3 comparisons are considered statistically significant at the 2-sided significance level of 0.05 and stop here; otherwise, go to Step 2.
- Step 2: If $p_{(2)}$ is ≤ 0.025 , then the corresponding 2 comparisons for $p_{(2)}$ and $p_{(1)}$ are considered statistically significant at the 2-sided significance level of 0.05 and stop here; otherwise, go to Step 3.
- Step 3: If $p_{(1)}$ is ≤ 0.01667 , then the corresponding comparison for $p_{(1)}$ is considered statistically significant at the 2-sided significance level of 0.05; otherwise, stop here.

Adjusted p-values using Hochberg procedure will also be provided.

13.0 Version History

Table 4. SAP Version History Summary

Version	Date	Summary
1.0	18 March 2020	Initial version
2.0	25 September 2023	This version of the SAP was completely re-written based on Protocol Amendment 5.
3.0	22 October 2024	
Corrected typos and inconsistencies throughout the document.
 
Removed the listing for positive urine pregnancy test per AbbVie CSR simplification standard.
 
For Japan submission purpose
 
 Section 3.3 added endpoints CFS in monthly headache days with nausea and/or vomiting symptom, photophobia and phonophobia Section 9.6 added efficacy subgroup analyses: number of migraine prevention medication failures with proven efficacy (category details below), migraine with or without aura diagnosis (migraine with aura, migraine without aura, and migraine both with and without aura), and prior exposure to calcitonin gene-related peptide (CGRP) antagonists (yes/no) 
Removed AESI summary by SOC and PT as data is not collected in the AE eCRF. Updated the text to refer to C-SSRS and lab section for summary.
 
Removed temperature from vital sign summary.
 
Updated SI unit and PCS low for estimated glomerular filtration rate in Table C-1 per standard lab transfer unit.
 
Added more details in estimand description and handling of the intercurrent events in Section 2.1, Section 9.3.2, and Section 9.4.2.

Appendix B. Derivation of Efficacy Variables and Health Outcome Endpoints

B.1 Derivation of Efficacy Endpoints Based on eDiary Data

A migraine day, a headache day, an acute medication use day, and a triptan use day are defined in Section 3.7 of the Operations Manual.

For analysis purposes, four weeks (28 days) will be considered as one month. On a daily basis during the 4-week baseline period and throughout the double-blind treatment period, subjects are to record eDiary information on the duration of headache, headache specific characteristics and symptoms, the pain severity, and use of any acute headache pain medication. Daily headache diary data consists of data from "today's diary" completed on that day and "yesterday's diary" completed on the following day. Subjects are to report headache data in "today's diary" in the evening at any time from 19:00 to 23:59 and to complete "yesterday's diary" on the following day to add the remaining headache data of previous evening until midnight. In case subjects miss "today's diary," they can report the whole-day headache data in "yesterday's diary" on the following day. In case subjects miss "yesterday's diary," headache data from "today's diary" alone will be used as daily headache diary data. If both "today's diary" and "yesterday's diary" are missing on one day, the daily headache diary data will be treated as missing.

Daily headache diary data will be merged from "today's diary" and "yesterday's diary" as following and will be used to derive migraine day and headache day.

- Daily headache total duration: summation of headache durations from "today's diary" and "yesterday's diary"
- Daily headache pain severity: the worst pain severity from "today's diary" and "yesterday's diary"
- Daily headache characteristics and symptoms: present if present in one of "today's diary" and "yesterday's diary"
- Daily acute headache medication usage: combination of acute headache medications usage from "today's diary" and "yesterday's diary."

- For the derivation of headache day, the subject is considered to have taken a non-antiemetic acute headache medication if the subject has taken such a medication in either "today's diary" or "yesterday's diary."

Moderate/severe headache day is defined as a headache day during which the maximum pain severity is either moderate or severe. Severe headache day is defined as a headache day during which the maximum pain severity is severe.

If a subject confirmed no headache for the Question 1 in eDiary, then the subject will not answer subsequent questions related to headache symptoms, duration, and acute headache medication use by design. Thus, the acute medication use for that diary ('today' or 'yesterday') will be treated as 'No' when deriving acute medication use day.

The monthly migraine days is defined as the total number of recorded migraine days in the eDiary divided by the total number of days with eDiary records during each monthly period and multiplied by 28. For baseline, a minimum of 20 days' eDiary data during the 4-week baseline period is required for the migraine days to be evaluable. For each postbaseline 4-week treatment period, a minimum of 14 days' eDiary data during that period is required for the migraine days to be evaluable. If a subject does not have at least 14 days of diary data for a monthly treatment period, the migraine days for that period will be considered as missing. Migraine days will be derived for each subject at baseline and for each postbaseline monthly treatment period (Weeks 1-4, 5-8, 9-12). The same method to derive monthly migraine days will be used to derive monthly headache days, monthly acute medication use days, monthly triptan use days, monthly cumulative headache hours, monthly moderate/severe headache days, and monthly severe headache days.

If a subject confirmed that acute medications were taken and entered medications in the eDiary, then the acute medication use day will be set to 'Yes.' If a subject reports 'Yes' to the intake of allowed medication(s) to treat an acute migraine but does not list any of them in the diary, then the acute medication use days will not be counted in this situation and vice versa.

B.2 Derivation of Health Outcome Endpoints

AIM-D Related Endpoints Derivation

The AIM-D was developed as a daily eDiary with a recall period of 24 hours. By design, it is collected in the today's diary only. The scoring of the following endpoints is completed in 2 steps.

- Monthly Performance of Daily Activities domain score of the AIM-D
- Monthly Physical Impairment domain score of the AIM -D
- Monthly AIM -D total score

Step 1: Calculate AIM-D daily domain score and total score

Daily performance of daily activities score will be calculated based on the summation of items 1-5 and 10 and 11, ranging from 0-35. A daily performance of daily activities domain score will be calculated if 4 or more item scores have non-missing responses. When the response category "I did not have <errands, leisure or social, strenuous activities> planned" (items 2, 4, and 5), is selected, the response will be considered missing. The corresponding performance of daily activities domain score will be calculated by summing the non-missing item scores and dividing by the number of non-missing items and then multiplying by 7, provided that 4 or more item scores are available; otherwise, it will be set to missing. The raw daily score will be transformed to a 0-100 scale by multiplying by 100 and dividing by the highest raw score (35).

Daily physical impairment scores will be calculated based on the summation of items 6-9, ranging from 0-20. A daily physical Impairment score will be calculated if 2 or more item scores have non-missing responses. The corresponding physical Impairment score will be calculated by summing the non-missing item scores and dividing by the number of non-missing items and then multiplying by 4, provided that 2 or more item scores are available; otherwise, it will be set to missing. The raw daily score will be transformed to a 0-100 scale by multiplying by 100 and dividing by the highest raw score (20).

A daily total score will be calculated based on the summation of items 1-11, ranging from 0-55. A Total Score will be calculated if 6 or more items scores have non-missing responses. When the response category "I did not have <errands, leisure or social, strenuous activities> planned" (items 2, 4, and 5), is selected, the response will be considered missing. The corresponding Total Score will be calculated by summing the non-missing item scores and dividing by the number of non-missing items and then multiplying by 11, provided that 6 or more item scores are available; otherwise, it will be set to missing. The raw score will be transformed to a 0-100 scale by multiplying by 100 and dividing by the highest raw score (55).

Step 2: Calculate Monthly Scores and Baseline Score

Monthly scores will be calculated using the average daily scores only if there are at least 14 non-missing daily scores in the corresponding monthly (28-day) period. The corresponding monthly scores will be calculated by summing the non-missing daily domain scores and dividing by the number of non-missing daily domain, provided that 14 or more daily scores are available; otherwise, it will be set to missing.

Activity Level and Activity Limitation

Monthly activity level score will be calculated by summing the non-missing daily scores and dividing by the number of these scores, provided that 14 or more daily scores are available in the corresponding monthly (28-day) period; otherwise, it will be set to missing. Same rule will be applied to the calculation of monthly activity limitation score.

MSQ Related Endpoints Derivation

MSQ v2.1 consists of 14 items with a 4-week recall period. The scoring of the MSQ is completed in following 3 steps.

Step 1: Final item value assignment.

Precoded item values and final item values for each MSQ item response are shown in Table B-1.

Table B-1. Item Values for MSQ Item Responses

Response Categories	Precoded Item Value	Final Item Value
None of the time	1	6
A little bit of the time	2	5
Some of the time	3	4
A good bit of the time	4	3
Most of the time	5	2
All of the time	6	1

Step 2: Computation of raw domain (dimension) scores.

Once a final item value has been assigned to each item, a raw score can be computed for each MSQ domain. Role Function Restrictive domain includes Items 1 - 7, Role Function Preventive domain includes Items 8 - 11, and Emotional Function domain includes Items 12 - 14. The raw score for each domain is the algebraic sum of the final item values for all items in that domain.

Missing data handling: if a respondent answered at least half of the items in a domain (or half plus one in the case of scales with an odd number of items), a missing item value can be estimated using the average of the other completed items within the same dimension.

In detail, for MSQ v2.1 Role Function Restrictive domain, the 7 individual item responses using final item value will be summed, resulting in the raw domain score ranging from 7 to 42 with higher scores indicating better quality of life. If there are missing item responses, the raw domain score will be calculated by summing the non-missing item responses using final item value and dividing by the number of non-missing items and then multiplying by 7 provided that 4 or more items in the domain are completed; otherwise it will be set to missing. For MSQ v2.1 Role Function Preventive and Emotional domains, the raw domain scores will be calculated similarly using final item

value respectively. If there are missing item responses, the corresponding raw domain score will be calculated by summing the non-missing item responses using final item value and dividing by the number of non-missing items and then multiplying by the number of questions in that domain provided that 2 or more domain items are completed; otherwise it will be set to missing.

Step 3: Linear transformation to a 0 to 100 scale.

The transformation formula for each MSQ 2.1 domain is listed below

- Role Function -Restrictive: $\frac{(raw\ score - 7) * 100}{35}$
- Role Function-Preventive: $\frac{(raw\ score - 4) * 100}{20}$
- Emotional Function: $\frac{(raw\ score - 3) * 100}{15}$

HIT-6 Total Score Derivation

For HIT-6 total score, pre-coded item values and final item values for each item response are shown in Table B-2. Total score is calculated by summing 6 sub-item responses, resulting in the total score ranging from 36 to 78 with higher scores indicating greater impact. If any sub item is missing, then total score will be missing.

Table B-2. Item Values for HIT-6 Item Responses

Response Categories	Precoded Item Value	Final Item Value
Never	0	6
Rarely	1	8
Sometimes	2	10
Very Often	3	11
Always	4	13

The HIT-6 instrument has a recall period of 4 weeks for 3 of the 6 items.

MIDAS Related Endpoints Derivation

MIDAS total score is derived as the sum of first 5 of questions (i.e., the sum of days missing work or school, Productivity at work or school reduced, Not do household work, Productivity in household work reduced, Miss family social or leisure activities). If any sub item is missing, the MIDAS total score will be missing.

The MIDAS absenteeism score is derived as the sum of Questions 1, 3 and 5. If any sub item is missing, then the MIDAS absenteeism score will be missing. The MIDAS presenteeism score is derived as the sum of Questions 2 and 4. If any sub item is missing, then the MIDAS presenteeism score will be missing.

WPAI:MIGRAINE Related Endpoints Derivation

WPAI outcomes are expressed as impairment percentages, with higher numbers indicating greater impairment and less productivity, i.e., worse outcomes, as follows:

Questions:

- Q1 currently employed (working for pay).
- Q2 missed work hours because of problems associated with your migraine
- Q3 missed work hours due to other reason.
- Q4 hours actually worked.
- Q5 migraine affected productivity while working.
- Q6 migraine affected regular daily activity.

Scores:

Multiply scores by 100 to express in percentages.

- Percent work time missed due to migraine (absenteeism): $Q2/(Q2 + Q4)$
- Percent impairment while working due to migraine (presenteeism): $Q5/10$
- Percent overall work impairment due to migraine (overall work productivity loss): $Q2/(Q2 + Q4) + (1 - (Q2/(Q2 + Q4))) \times (Q5/10)$
- Percent activity impairment due to migraine (regular activity impairment): $Q6/10$

If the response to Q1 ("Currently employed?") is No or missing, absenteeism, presenteeism, and overall work productivity loss will all be set to missing.

EQ-5D-5L Score Derivation

The EQ-5D-5L is made up of two components: health state description and evaluation. The description component consists of five dimensions: mobility, self-care, usual activities, pain/discomfort, and anxiety/depression. The mobility dimension queries the subject's walking ability. The self-care dimension queries the subject's ability to wash or dress by himself. The usual activities dimension assesses the subject's performance in "work, study, housework, family or leisure activities." The pain/discomfort dimension measures how much pain or discomfort a subject has. The anxiety/depression dimension assesses how anxious or depressed a subject is. The respondents rate their level of severity for each dimension using a 5-level scale (EQ-5D-5L) by ticking (or placing a cross) in the box against the most appropriate statement in each of the 5 dimensions. The second component of the EQ-5D-5L is a visual analogue scale (EQ-VAS) by which subjects can rate their overall health from 0 (worst imaginable health state) to 100 (best imaginable health state).

With the EQ-5D-5L, rating levels can be coded as numbers 1, 2, 3, 4 or 5 which correspond to "have no problems," "have slight problems," "have moderate problems,"

"have severe problems," and "unable to do/have extreme problems," respectively. As a result, a subject's health state can be defined by a 5-digit number by combining the numeric levels from the 5 dimensions, ranging from 11111 ("have no problems" in all 5 dimensions) to 55555 ("unable to do/have extreme problems" in all 5 dimensions). The index value for the EQ-5D-5L will be derived using an international standardized protocol.

EQ-5D-5L will be captured on eDiary during 7 days in the screening/baseline period and during specific time periods for Visit 1 to 5. The index score and VAS score for a specific period will be calculated as the average of available scores in that period respectively if at least 50% of daily scores are available; otherwise, the scores will be set as missing. For example, for a period of 14 days, at least 7 assessments are required; and for a period of 7 days, at least 4 assessments are required.

PROMIS-PI T-Score Derivation

The PROMIS-PI measures self-reported interference of pain on relevant aspects of daily life (i.e., social, cognitive, emotional, physical, recreational) over the past 7 days. A 5-level response scale for all 6 items ranges from 1 to 5, corresponding to item response of "Not at all" to "Very much." The raw score of PROMIS-PI is the sum of all 6 items, ranging from 6 to 30. If one or more items are missing, the raw score will be set to missing. A raw score can be standardized into a T-score with a mean of 50 and standard deviation of 10 using Table B-3. Higher raw or T-scores indicate greater pain interference.

Table B-3. PROMIS-PI Raw Score Transformation

Raw Score	T-Score	Raw Score	T-Score	Raw Score	T-Score	Raw Score	T-Score
6	41.1	13	56.6	20	63.0	27	69.8
7	48.6	14	57.6	21	63.8	28	71.0
8	50.7	15	58.6	22	64.8	29	72.6
9	52.2	16	59.5	23	65.7	30	76.3
10	53.4	17	60.4	24	66.7		
11	54.5	18	61.2	25	67.6		
12	55.6	19	62.1	26	68.7		

Patient Health Questionnaire (PHQ-9)

The PHQ-9 consists of the 9 diagnostic criteria for depressive disorders in the past 2 weeks from the DSM-IV. Subjects are asked to indicate the frequency with which they have been bothered by 9 symptoms of depressive disorders over the previous 2 weeks, on a 4-point scale: 0 (not at all), 1 (several days), 2 (more than half the days), and 3 (nearly every day). The total score ranges from 0 to 27 (from best to worst). A score of 15 to 19 is considered as moderately severe depression and 20 to 27 as severe depression. A Total Score will be calculated using $(\text{sum of non-missing items}) \times 9 / (\text{number of non-missing items})$ if 5 or more items scores have non-missing responses.

Appendix C. Potentially Clinically Significant Criteria for Safety Endpoints

The criteria for Potentially Clinically Significant (PCS) laboratory findings are described in Table C-1 and Table C-2. The PCS criteria for vital sign findings are described in Table C-3, and the PCS criteria for ECG parameters are described in Table C-4.

Table C-1. Potentially Clinically Significant Criteria for Clinical Laboratory Parameters

Category	Parameter	SI Unit	PCS Criteria	
			PCS Low	PCS High
Chemistry	Albumin	g/L	$< 0.8 \times \text{LLN}$	$> 1.2 \times \text{ULN}$
	Alanine aminotransferase	U/L	—	$\geq 3.0 \times \text{ULN}$
	Alkaline phosphatase	U/L	—	$\geq 3.0 \times \text{ULN}$
	Aspartate aminotransferase	U/L	—	$\geq 3.0 \times \text{ULN}$
	Bicarbonate	mmol/L	$< 0.9 \times \text{LLN}$	$> 1.1 \times \text{ULN}$
	Bilirubin, total	$\mu\text{mol/L}$	—	$\geq 1.5 \times \text{ULN}$
	Blood urea nitrogen	mmol/L	—	$> 1.5 \times \text{ULN}$
	Calcium	mmol/L	$< 0.9 \times \text{LLN}$	$> 1.1 \times \text{ULN}$
	Chloride	mmol/L	$< 0.9 \times \text{LLN}$	$> 1.1 \times \text{ULN}$
	Cholesterol, total	mmol/L	—	$> 1.6 \times \text{ULN}$
	Creatinine	$\mu\text{mol/L}$	—	$> 1.5 \times \text{ULN}$
	Creatine kinase	U/L	—	$> 2.0 \times \text{ULN}$
	Estimated glomerular filtration rate	mL/sec/1.73m^2	< 1	—
	Glucose, nonfasting	mmol/L	$< 0.8 \times \text{LLN}$	$> 2.0 \times \text{ULN}$
	Lactate dehydrogenase (LDH)	U/L	—	$> 3.0 \times \text{ULN}$
	Phosphorus	mmol/L	$< 0.9 \times \text{LLN}$	$> 1.1 \times \text{ULN}$
	Potassium	mmol/L	$< 0.9 \times \text{LLN}$	$> 1.1 \times \text{ULN}$
	Protein, total	g/L	$< 0.9 \times \text{LLN}$	$> 1.1 \times \text{ULN}$
	Sodium	mmol/L	$< 0.9 \times \text{LLN}$	$> 1.1 \times \text{ULN}$
	Triglycerides	mmol/L	—	$> 2.0 \times \text{ULN}$
	Uric acid	$\mu\text{mol/L}$	—	$> 1.2 \times \text{ULN}$

Category	Parameter	SI Unit	PCS Criteria	
			PCS Low	PCS High
Hematology	Basophils, absolute cell count	$10^9/L$	—	$> 2.0 \times ULN$
	Eosinophils, absolute cell count	$10^9/L$	—	$> 2.0 \times ULN$
	Hematocrit	Ratio	$< 0.9 \times LLN$	$> 1.1 \times ULN$
	Hemoglobin	g/L	$< 0.9 \times LLN$	$> 1.1 \times ULN$
	Lymphocytes, absolute cell count	$10^9/L$	$< 0.7 \times LLN$	$> 1.3 \times ULN$
	Monocytes, absolute cell count	$10^9/L$	$< 0.5 \times LLN$	$> 2.0 \times ULN$
	Neutrophils, absolute cell count	$10^9/L$	$< 0.7 \times LLN$	$> 1.3 \times ULN$
	Platelet count	$10^9/L$	$< 0.5 \times LLN$	$> 1.5 \times ULN$
	Red blood cell count	$10^{12}/L$	$< 0.9 \times LLN$	$> 1.1 \times ULN$
	White blood cell count	$10^9/L$	$< 0.9 \times LLN$	$> 1.5 \times ULN$
Urinalysis	pH	pH	$< 0.9 \times LLN$	$> 1.1 \times ULN$
	Glucose	mmol/L	—	Positive ¹
	Protein	g/L	—	Positive ²
	Specific gravity	—	—	$> 1.1 \times ULN$

LLN = lower limit of normal value; ULN = upper limit of normal value; normal value provided by laboratory.

SI = Le Système International d'Unités (International System of Units).

- Any results other than negative will be considered as positive.
- Any results other than trace or negative will be considered as positive.

Table C-2. Criteria for Hepatic Laboratory Abnormalities

Laboratory Parameter	Categories
ALT	$\geq 1 \times ULN$
	$\geq 1.5 \times ULN$
	$\geq 2 \times ULN$
	$\geq 3 \times ULN$
	$\geq 5 \times ULN$
	$\geq 10 \times ULN$
	$\geq 20 \times ULN$

Laboratory Parameter	Categories
AST	$\geq 1 \times \text{ULN}$ $\geq 1.5 \times \text{ULN}$ $\geq 2 \times \text{ULN}$ $\geq 3 \times \text{ULN}$ $\geq 5 \times \text{ULN}$ $\geq 10 \times \text{ULN}$ $\geq 20 \times \text{ULN}$
ALT or AST	$\geq 1 \times \text{ULN}$ $\geq 1.5 \times \text{ULN}$ $\geq 2 \times \text{ULN}$ $\geq 3 \times \text{ULN}$ $\geq 5 \times \text{ULN}$ $\geq 10 \times \text{ULN}$ $\geq 20 \times \text{ULN}$
Bilirubin Total	$\geq 1 \times \text{ULN}$ $\geq 1.5 \times \text{ULN}$ $\geq 2 \times \text{ULN}$ $\geq 3 \times \text{ULN}$ $\geq 5 \times \text{ULN}$ $\geq 10 \times \text{ULN}$ $\geq 20 \times \text{ULN}$
Alkaline Phosphatase	$\geq 1 \times \text{ULN}$ $\geq 1.5 \times \text{ULN}$ $\geq 2 \times \text{ULN}$ $\geq 3 \times \text{ULN}$ $\geq 5 \times \text{ULN}$ $\geq 10 \times \text{ULN}$ $\geq 20 \times \text{ULN}$
Concurrent Elevations ¹	ALT or AST $\geq 3 \times \text{ULN}$ and Bilirubin Total $\geq 1.5 \times \text{ULN}$ ALT or AST $\geq 3 \times \text{ULN}$ and Bilirubin Total $\geq 2 \times \text{ULN}$

Laboratory Parameter	Categories
Potential Hy's Law ¹	ALT or AST $\geq 3 \times$ ULN and Bilirubin Total $\geq 2 \times$ ULN and ALP $< 2 \times$ ULN

ALT alanine aminotransferase; AST aspartate aminotransferase; TBL total bilirubin; ALP alkaline phosphatase; ULN upper limit of normal (value provided by the laboratory)

1. Elevations are from the same day

Vital sign values will be considered PCS if they meet both the observed value criterion and the change from baseline value criterion, if both criteria are available, or meet either the observed value criterion or the change from baseline value criterion that is detailed in the following table.

Table C-3. Potentially Clinically Significant Criteria for Vital Signs Parameters

Parameter	Flag	Criteria	
		Observed Value	Change from Baseline
Systolic blood pressure, mm Hg	High	≥ 180	Increase of ≥ 20
	Low	≤ 90	Decrease of ≥ 20
Diastolic blood pressure, mm Hg	High	≥ 105	Increase of ≥ 15
	Low	≤ 50	Decrease of ≥ 15
Pulse rate, bpm	High	≥ 120	Increase of ≥ 15
	Low	≤ 50	Decrease of ≥ 15
Weight, kg	High	—	Increase of $\geq 7\%$
	Low	—	Decrease of $\geq 7\%$
Orthostatic SBP change, mm Hg	Low	≤ -20	—
Orthostatic DBP change, mm Hg	Low	≤ -15	—
Orthostatic Pulse rate change, bpm	High	≥ 25	—

SBP Systolic blood pressure; DBP Diastolic blood pressure; bpm beats per minute

ECG parameter values are considered PCS if ECG values meet either the actual value or change from baseline PCS high criteria listed in the following table.

Table C-4. Potentially Clinically Significant Criteria for ECG Parameters

Parameter	Unit	Criterion
QRS interval	msec	≥ 150
PR interval	msec	≥ 250
QTc (QTcB or QTcF) interval	msec	> 500
QTc (QTcB or QTcF) interval	msec	Increase from baseline > 60

Table C-5. ECG Post-baseline Values of Clinical Interest

Parameter	Unit	Criterion
QTcF	msec	> 450
		> 480
		> 500
		Increase > 30 but ≤ 60
		Increase > 60

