10.3 Analysis of Laboratory Data

The clinical laboratory tests defined in the protocol operations manual (e.g., hematology, clinical chemistry, and urinalysis) will be summarized.

Each laboratory variable will be summarized by treatment group for all time points (starting with Baseline) with the number of non-missing observations, mean and standard deviation, median, Q1, Q3, minimum and maximum. Mean change from baseline to each applicable post-baseline visit will be summarized for selected laboratory variables, with the number of observations, baseline mean, and visit mean. In addition, descriptive statistics for values and changes from the baseline values in conventional units at each assessment time point will be presented for selected clinical laboratory parameters listed in [Appendix D](#). A description of reporting the lab values in conventional units in patient narratives (along with the standard reporting in SI units) is presented at the end of [Appendix D](#).

Laboratory abnormalities will be evaluated based on Potentially Clinically Significant (PCS) criteria ([Appendix C](#), Table C-1). For each laboratory PCS criterion, the number

and percentage of subjects who have a laboratory value meeting the criteria will be summarized by treatment group. Listings will be provided to summarize subject-level laboratory data for subjects meeting PCS criteria.

The number and percentage of subjects meeting each of the criteria for postbaseline hepatic laboratory abnormalities listed in [Appendix C](#), Table C-2 will be summarized. The percentages will be calculated relative to the number of subjects with at least 1 available postbaseline assessment. The numerator will be the total number of subjects having at least 1 postbaseline value that meets the specific category during the study. A supportive listing will also be provided.

The number and percentage of subjects with an adjudicated case (i.e., $ALT \geq 3 \times ULN$ and/or $AST \geq 3 \times ULN$) will be summarized by treatment group and by relationship of ALT or AST elevation to study medication. The percentages will be calculated relative to the number of subjects with at least 1 adjudicated case. The numerator will be the number of subjects with at least 1 adjudicated case in the specific category of relationship. If a subject has more than 1 adjudicated case, he or she will be counted in the most relevant category of relationship.

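### The SAP's PCS threshold for urine specific gravity (1.1 × ULN) is at least 1.100, so no genuine urine value is expected to meet it and the row is a structural zero

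*SAP*

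**What the plan says.** The urinalysis block of Table C-1 (SAP Appendix C) has this row: "Specific gravity — — $> 1.1 \times ULN". The two dashes mean that the row has no unit and no PCS Low criterion, so everything depends on the upper threshold. The table's footnote defines the limit: "ULN = upper limit of normal value; normal value provided by laboratory". No footnote applies the multiplier to another scale, such as the excess over 1.

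SAP Section 10.3 puts urinalysis within the laboratory summaries ("e.g., hematology, clinical chemistry, and urinalysis) will be summarized"). The sentence beginning "For each laboratory PCS criterion, the number" promises a count and percentage by treatment group of subjects who meet each criterion, and subject-level listings follow. The same section has a second, separate display: "Each laboratory variable will be summarized by treatment group for all time" points, with the minimum and maximum among the statistics.

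**The concern.** A multiple of the ULN works as a rule for extreme values when the quantity is measured from zero. Table C-1 applies the same factor of 1.1 to sodium, potassium and hemoglobin, where 10% above the limit is a value that can occur. Specific gravity is a ratio to water, so its information lies in the digits after 1. Adding 10% to the whole number moves the threshold by at least 0.1, which is large on that scale.

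At stake is how one line of the safety tables will be read. A row showing 0% in all arms suggests that the parameter was checked and nothing was found. If the criterion cannot be met, the zero carries no information about the drug.

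**Working it through.** **Inputs**

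- Criterion: value > 1.1 × ULN (SAP Table C-1).
- ULN: set by the laboratory, with no figure in the documents. Assumed range 1.020 to 1.040, with water (1.000) as the floor.
- Highest genuine urine value: not in the documents. Assumed values from 1.035 to 1.080.

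The plan states no numeric threshold, so there is no figure of its own to reproduce.

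**Step 1. Threshold = 1.1 × ULN**

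| ULN | Threshold |
|---|---|
| 1.000 (floor) | 1.100 |
| 1.020 | 1.122 |
| 1.025 | 1.1275 |
| 1.030 | 1.133 |
| 1.035 | 1.1385 |
| 1.040 | 1.144 |

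The lowest possible threshold is 1.1 × 1.000 = 1.100. The result therefore does not depend on which ULN the laboratory supplies.

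**Step 2. ULN that would be needed for a given value to be flagged**

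A value m is flagged only if ULN < m / 1.1.

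| Assumed maximum m | ULN must be below |
|---|---|
| 1.035 | 0.9409 |
| 1.040 | 0.9455 |
| 1.050 | 0.9545 |
| 1.060 | 0.9636 |
| 1.080 | 0.9818 |
| 1.100 | 1.0000 |

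For every assumed maximum from 1.035 to 1.080, the ULN would have to be less than the specific gravity of water.

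**Step 3. Distance from the threshold**

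With an assumed ULN of 1.030, a reading of 1.050 is 1.050 / 1.030 = 1.019 times the ULN, and 1.080 is 1.080 / 1.030 = 1.049 times the ULN. Both are well short of 1.1.

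**Step 4. What else uses the row**

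The adverse events of special interest (protocol Section 6.1, SAP Section 10.2.5) concern suicidality, ALT/AST elevation and potential Hy's law cases. The liver-related interruption criteria in protocol Section 5.5 use ALT, AST, bilirubin, INR and symptoms or signs. Withdrawal for other abnormal laboratory results in that section rests on the judgement of the investigator or sponsor, not on Table C-1. The Hochberg procedure covers only the three dose comparisons on the primary endpoint.

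**The case against.** The strongest objection is that the deciding premise comes from outside the documents. They give no range for urine specific gravity and no ULN, and Section 10.3 leaves the test definitions to the operations manual, which was not available here. That is right about the urine maximum, which must be stated as an assumption. It does not rescue the row for any maximum in the range tried. The missing ULN does not matter, because of the 1.100 floor.

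A second objection is that a PCS threshold is meant to be a high bar. A high bar still has to be reachable. Table C-1 itself drops multiples where they do not suit the parameter: urine glucose and protein are judged positive or not, and eGFR has an absolute cut-off.

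Three stronger readings are tempting and are not supported:

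- A reader might infer that abnormal specific gravity would go unseen. Section 10.3 reports each laboratory variable at all time points with its maximum, so a shift or an extreme value would still show. Only the flag count and its listing are lost.
- A reader might infer that the row is zero whatever happens. A transcription or unit error could still trigger it. The claim is limited to genuine urine values.
- A reader might add that laboratory methods cannot read values this high. The documents say nothing about the assay, and the point does not need it.

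**Conclusion.** The criterion is wrong as written, with a small effect. For any laboratory ULN of at least 1.000 the threshold is 1.100 or more. On the assumption that genuine urine values stay below 1.100, the PCS count for specific gravity is 0% in every arm by construction, and the listing will contain no subject because of a genuine specific-gravity value.

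The consequence is one uninformative line in the descriptive safety output. Efficacy conclusions, Type I error control, the hepatic analyses and the adverse events of special interest are unaffected. The assumption about the urine maximum is the only one that the conclusion needs from outside the documents.

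**What to change.** Either of two changes to Table C-1 is enough.

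1. **Delete the specific-gravity row.** This is complete as it stands and loses nothing, because the descriptive summaries in Section 10.3 remain.
2. **Have the sponsor restate the row on a scale the variable can reach.** One example is a count of subjects with a value above the laboratory ULN, labelled as out of range. Its small downside is a lower bar than the other rows: every other numeric PCS High multiple in the table exceeds 1 × ULN, hence the separate label. A criterion on the excess over 1.000 would also work, but the sponsor would have to choose and state the multiple.

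The cost is one table cell or row in the SAP and the matching table shell, with no new data. There is a precedent: according to the SAP's version history, version 3.0 already revised the eGFR entry in the same table.
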